7.3.6. Completion (discontinuation) record

If the observation is completed or discontinued before the end of the longest observation period (16 weeks), the reason should be recorded.

If an adverse event is selected for the reason, the information in details should be recorded in the adverse event column.

[Reason for completion]
- Cured (effective)

[Reason for discontinuation]
- Insufficient clinical effectiveness

- Adverse events
- No revisit
- Hospital transfer
- Other

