7.3.7. Effectiveness evaluation

7.3.7.1. Clinical response

The clinical response of this product should be evaluated based on the clinical course excluding the mycological response at the end of the observation period.

If this product is used continuously for more than 16 weeks, the clinical response should be evaluated comprehensively at Week 16.

- Effective
- Not effective
- Indeterminate (In this case, the reason should be recorded.)

Reason in the case of indeterminate

- Because the diagnosis is not "invasive fungal infections" or "invasive fungal infections suspected"
- Other

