5.4. Subgroups

Subgroup analyses of safety will be performed for the following patient background factors. Levels in parentheses are levels of subgroups, and underlined levels are the reference for calculation of risk ratio and risk difference.

- Hepatic dysfunction [absent, present]
- Renal dysfunction [absent, present]
- Age (children 1) [newborns (<1 month after birth), infants (≥ 1 month to <1 year), younger children (≥ 1 to <7 years), children (≥ 7 to <15 years)]
- Age (children 2) [<2 years, ≥ 2 years]
- Diagnostic name (name of infection) [invasive aspergillosis, pulmonary aspergilloma, chronic necrotic pulmonary aspergillosis, candidemia, esophageal candidiasis, candida peritonitis, bronchopulmonary candidiasis, cryptococcal meningitis, pulmonary cryptococcosis, fusariosis, scedosporiosis, other invasive fungal infections, others]
- Severity [mild, moderate, severe]
- Fever unresponsive to antibacterial agents [absent, present]
- Use of concomitant medications requiring precautions for coadministration [absent, present]
- Concomitant antifungal agents [absent, present]
- Prior medications (antifungal agents) [absent, present]
- Treatment period [<1 week, ≥ 1 to <2 weeks, ≥ 2 to <4 weeks, ≥ 4 to <8 weeks, ≥ 8 to <12 weeks, ≥ 12 to ≤ 16 weeks]
- Long-term treatment [≤ 12 weeks, >12 weeks]
- Dose on the first day (mg/kg) [<6, ≥ 6 to <7, ≥ 7 to <8, ≥ 8 to <9, ≥ 9 to <10, ≥ 10 , unknown]
- Mean maintenance dose (mg/kg) [<6, ≥ 6 to <7, ≥ 7 to <8, ≥ 8 to <9, ≥ 9 to <10, ≥ 10 , unknown]

Subgroup analyses of safety will be performed for the following:

- Pregnant and parturient women (pregnancy confirmed)
- Presence or absence of overdose^a

Patients who may meet contraindications in the package insert of Vfend (hereinafter referred to as contraindicated patients) will be extracted based on separately specified criteria, and subgroup analyses of safety will be performed.

Subgroup analyses of efficacy (clinical response) will be performed for the following patient background factors. Levels in parentheses are levels of subgroups, and underlined levels are the reference for calculation of risk ratio and risk difference.

- Hepatic dysfunction [absent, present]
- Renal dysfunction [absent, present]
- Age (children 1) [newborns (<1 month after birth), infants (≥ 1 month to <1 year), younger children (≥ 1 to <7 years), children (≥ 7 to <15 years)]
- Age (children 2) [<2 years, ≥ 2 years]

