- Diagnostic name (name of infection) [invasive aspergillosis, pulmonary aspergilloma, chronic necrotic pulmonary aspergillosis, candidemia, esophageal candidiasis, candida peritonitis, bronchopulmonary candidiasis, cryptococcal meningitis, pulmonary cryptococcosis, fusariosis, scedosporiosis, other invasive fungal infections, others]
- Severity [mild, moderate, severe]
- Fever unresponsive to antibacterial agents [absent, present]
- Use of concomitant medications requiring precautions for coadministration [absent, present]
- Concomitant antifungal agents [absent, present]
- Prior medications (antifungal agents) [absent, present]
- Treatment period [<1 week, ≥ 1 to <2 weeks, ≥ 2 to <4 weeks, ≥ 4 to <8 weeks, ≥ 8 to <12 weeks, ≥ 12 to ≤ 16 weeks]
- Long-term treatment [≤ 12 weeks, >12 weeks]
- Dose on the first day (mg/kg) [<6, ≥ 6 to <7, ≥ 7 to <8, ≥ 8 to <9, ≥ 9 to <10, ≥ 10 , unknown]
- Mean maintenance dose (mg/kg) [<6, ≥ 6 to <7, ≥ 7 to <8, ≥ 8 to <9, ≥ 9 to <10, ≥ 10 , unknown]

^a : Because the upper limit of the dose of oral preparations (tablet and dry syrup) is 350 mg according to the dosage and administration of Vfend in children (aged ≥ 2 to <12 years and ≥ 12 years and weighing <50 kg), patients receiving oral preparations at a dose of >350 mg are defined as overdosed. Although there is no upper limit for injection, patients receiving injection at a dose of >350 mg and ≥ 10 mg/kg are defined as overdosed.

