8.1.3. Analysis of Binary Data

The number of patients and proportion will be calculated. If the confidence interval of proportion is calculated, two-sided 95% confidence interval (exact method) will be calculated.

If the proportion is compared between subgroups, risk ratio and its 95% confidence interval, and risk difference and its 95% confidence interval will be calculated. In addition, risk ratio and its 95% confidence interval will be graphically presented (see Appendix 2). If the number of patients in each subgroup compared is ≤ 5 , the number of patients and proportion will be calculated but risk ratio and its 95% confidence interval, and risk difference and its 95% confidence interval will not be calculated.

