In the safety analysis set, clinical response analysis set, and mycological response analysis set, the number and proportion of the following patients will be tabulated.

- Concomitant medications
- Contraindicated concomitant medications
- Concomitant medications requiring precautions for coadministration
- Prior treatment (antifungal agents) for infection for which Vfend is administered
- Reasons for discontinuation of prior treatment for infection for which Vfend is administered

- **Status of treatment of Vfend**

In the safety analysis set, the following status of treatment of Vfend will be tabulated: Furthermore, dose will be tabulated separately for patients aged <12 years and ≥12 years

whose body weight is less than 50 kg and those aged ≥ 12 years whose body weight is 50 kg or more.

- Treatment period [<1 week, ≥ 1 to <2 weeks, ≥ 2 to <4 weeks, ≥ 4 to <8 weeks, ≥ 8 to <12 weeks, ≥ 12 to ≤ 16 weeks, >16 weeks]
- Treatment period (long-term treatment) [≤ 12 weeks, >12 weeks]
- Treatment period (days) (continuous)
- Dose on the first day (mg) (continuous)
- Dose on the first day (mg) [<50 , ≥ 50 to <100 , ≥ 100 to <150 , ≥ 150 to <200 , ≥ 200 to <250 , ≥ 250 to <300 , ≥ 300 to <350 , ≥ 350 , unknown]
- Dose on the first day (mg/kg) (continuous)
- Dose on the first day (mg/kg) [<6 , ≥ 6 to <7 , ≥ 7 to <8 , ≥ 8 to <9 , ≥ 9 to <10 , ≥ 10 , unknown]
- Mean maintenance dose (mg) (continuous)
- Mean maintenance dose (mg) [<50 , ≥ 50 to <100 , ≥ 100 to <150 , ≥ 150 to <200 , ≥ 200 to <250 , ≥ 250 to <300 , ≥ 300 to <350 , ≥ 350 , unknown]
- Mean maintenance dose (mg/kg) (continuous)
- Mean maintenance dose (mg/kg) [<6 , ≥ 6 to <7 , ≥ 7 to <8 , ≥ 8 to <9 , ≥ 9 to <10 , ≥ 10 , unknown]
- Mean maintenance dose of injection alone (mg) (continuous)
- Mean maintenance dose of injection alone (mg) [<50 , ≥ 50 to <100 , ≥ 100 to <150 , ≥ 150 to <200 , ≥ 200 to <250 , ≥ 250 to <300 , ≥ 300 to <350 , ≥ 350 , unknown]
- Mean maintenance dose of injection alone (mg/kg) (continuous)
- Mean maintenance dose of injection alone (mg/kg) [<6 , ≥ 6 to <7 , ≥ 7 to <8 , ≥ 8 to <9 , ≥ 9 to <10 , ≥ 10 , unknown]
- Mean maintenance dose of oral preparations (tablet + dry syrup) alone (mg) (continuous)
- Mean maintenance dose of oral preparations (tablet + dry syrup) alone (mg) [<50 , ≥ 50 to <100 , ≥ 100 to <150 , ≥ 150 to <200 , ≥ 200 to <250 , ≥ 250 to <300 , ≥ 300 to <350 , ≥ 350 , unknown]

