- Mean maintenance dose of oral preparations (tablet + dry syrup) alone (mg/kg) (continuous)
- Mean maintenance dose of oral preparations (tablet + dry syrup) alone (mg/kg) [<6 , ≥ 6 to <7 , ≥ 7 to <8 , ≥ 8 to <9 , ≥ 9 to <10 , ≥ 10 , unknown]

The treatment period is from the initial day of administration in this study to the last confirmed day of administration, including the period during which Vfend is suspended.

If treatment with Vfend is continued at the end of the observation period, the treatment period will be considered as 113 days because Vfend is administered for >16 weeks (Week 16 is up to Day 112 with the day of initiation of treatment considered as Day 1).

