8.2.3. Safety Analysis

Adverse drug reactions and adverse events observed during the observation period (from the day of initiation of Vfend treatment to the day of completion of treatment) + follow-up period (28 days*) or if the treatment prolongs, during the period from the initiation of treatment to Week 16 (Day 112 counting from Day 1 as the day the treatment begins) will be tabulated. If the duration of the observation period + follow-up period exceeds 112 days, events observed by Day 112 will be tabulated. All events reported in this study will be included in listings.

*: The duration of the follow-up period in this investigation was set at 28 days because a 30-day follow-up period was provided in a clinical study (Study A1501096) and the period of collection of adverse events using NIS AE Report Form in this investigation is up to 28 days after the day of completion of treatment.

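### SAP 5.4 has no Treatment period level for patients set to 113 days, and both treatment-duration factors get crude risk ratios although reactions, cure and failure end treatment

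*SAP*

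**What the plan says.** **Levels.** In SAP 5.4, for both safety and clinical response, Treatment period ends with "≥ 8 to <12 weeks, ≥ 12 to ≤ 16 weeks". SAP 8.2.2 lists the same variable with a seventh level, "≥ 12 to ≤ 16 weeks, >16 weeks". For patients still on treatment at the end of observation it adds that "the treatment period will be considered as 113 days because Vfend is administered for >16 weeks". The second duration factor, Long-term treatment, has two levels split at 12 weeks.

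**Analysis.** SAP 5.4 introduces these as background factors: "Subgroup analyses of safety will be performed for the following patient background factors". SAP 8.2.3.4 applies the method of 8.1.3 to each of them: "If the proportion is compared between subgroups, risk ratio and its 95% confidence interval", together with the risk difference. No covariates are named (SAP 6.4). SAP 8.2.3.5 then tabulates reactions further for factors with a risk ratio of at least 2 or at most 0.5. SAP 8.2.4.4 applies the 5.4 factors to clinical response, without such a screen.

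**What determines duration.** Protocol 7.3.6 gives cure as the reason for completion. Its reasons for discontinuation include adverse events and "Insufficient clinical effectiveness".

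**Counting window.** SAP 8.2.3 counts reactions during treatment plus 28 days: "If the duration of the observation period + follow-up period exceeds 112 days, events observed by Day 112 will be tabulated".

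**Response in long-treated patients.** Protocol 7.3.7.1: "If this product is used continuously for more than 16 weeks, the clinical response should be evaluated comprehensively at Week 16".

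**The concern.** Patients treated beyond the cut-off have reaction data to Day 112 and a Week 16 response, but as written they drop out of the Treatment period subgroup tables. Nothing tells the programmer to fold them into the top level, and 8.2.2 keeps them apart.

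The second problem is interpretive. A subgroup factor is useful for finding risk factors if it is settled before the outcome. Here the outcome helps settle the factor. A reaction that stops treatment moves the patient into a short-duration level, which pulls the risk ratio for long treatment down. A longer treatment gives more days on which a reaction can be counted, which pulls it up. For clinical response, cure and failure are themselves reasons for stopping, so duration partly restates the response. Identifying factors that affect safety and effectiveness is a stated objective (Protocol 6), so a reader could take these ratios for findings.

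**Working it through.** **1. Level check.** 112/7 = 16.0 weeks, inside the top 5.4 level. 113/7 = 16.14 weeks, outside it. The 5.4 Treatment period lists have no unknown level either.

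**2. Counting window.** With last treatment day d, the window closes on min(d + 28, 112).
- Under 1 week (d = 1 to 6): Day 29 to Day 34.
- 12 weeks or more (d ≥ 84): 84 + 28 = Day 112.

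**3. Window alone.** Assume a constant reaction hazard, the same on and off treatment, with no reaction stopping treatment. With 28-day risk p, the risk by Day t is R(t) = 1 − (1 − p)^(t/28).

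| p (assumed) | R(29) | R(34) | R(112) | Ratio, ≥12 weeks vs <1 week |
|---|---|---|---|---|
| 30% | 0.309 | 0.352 | 0.760 | 0.760/0.352 = 2.16 to 0.760/0.309 = 2.46 |
| 50% | 0.512 | 0.569 | 0.938 | 0.938/0.569 = 1.65 to 0.938/0.512 = 1.83 |

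**4. Window and stopping together.** The documents give no onset pattern, stopping share or duration distribution, so all of these are assumed:
- exponential planned duration, median 21, 35 or 56 days, set to 113 if beyond Day 112;
- onset either at constant hazard (28-day risk 30% or 50%) or early (half the patients susceptible, median onset 3 or 7 days);
- 0 to 70% of on-treatment reactions stop treatment;
- the reaction hazard is the same on and off treatment, so there is no true effect.

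Each scenario used 1,000,000 simulated patients. Results at median 35 days, by share of reactions stopping treatment:

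| Comparison | Onset | 0% | 10% | 50% | 70% |
|---|---|---|---|---|---|
| >12 vs ≤12 weeks | constant, 30% | 1.49 | 1.43 | 1.18 | 0.99 |
| | constant, 50% | 1.27 | 1.26 | 1.17 | 1.09 |
| | early, 3 days | 1.00 | 0.94 | 0.63 | 0.43 |
| | early, 7 days | 1.01 | 0.95 | 0.64 | 0.44 |
| 12-16 vs <1 week | constant, 30% | 2.31 | 2.03 | 1.41 | 1.19 |
| | constant, 50% | 1.74 | 1.59 | 1.27 | 1.17 |
| | early, 3 days | 0.99 | 0.77 | 0.41 | 0.28 |
| | early, 7 days | 1.04 | 0.85 | 0.46 | 0.30 |

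Over all three medians, >12 versus ≤12 weeks spans about 0.40 to 1.60, and 12-16 versus <1 week about 0.3 to 2.3. The <1 week reference is an assumption, because the underlining that marks reference levels is lost from the text.

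The upper ends depend on the assumed reaction rate. A separate run with a lower rate (16-week risk 30% or 50%, medians 28 and 56 days, 0 to 50% stopping) reached 1.85 and 3.21.

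**5. Studies of 100 patients**, median 35 days. Chance is gauged by shuffling reactions between patients.
- Long-term treatment, early onset: the ratio is 0.5 or less in 2% of studies with no stopping, 4% at 10%, 30-31% at 50% and 64% at 70%. Chance gives 2-5%.
- Six-level Treatment period, at least one comparison outside the limits: constant 30% hazard with no stopping, 77% against 27% by chance; early 7-day onset with no stopping, 39% against 37%.

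**6. Patients at 113 days.** About 4-11 of 100 at median 35 days, and 1-25 over the three medians.

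**The case against.** The strongest reply is that little hangs on these ratios. SAP 4.1 calls the work exploratory with no significance level, 4.2 has no decision rule, and the 8.2.3.5 screen leads only to further tables. Additional exploratory results are reported only if they matter for interpretation. SAP 8.1.3 suppresses ratios in very small subgroups, 8.2.3.1 already plans onset tables and Kaplan-Meier summaries for the major items and common reactions, and Protocol 7.9 admits that confounding may be poorly handled. All of this stands and limits the harm. None of it removes the bias or supplies the missing level.

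Four stronger readings are tempting and not supported:
- **That artefact alone will often push Long-term treatment past the screen.** In the step 4 scenarios the population ratio never reaches 2, and it falls to 0.5 or less only near 70% stopping, a share no section supports. At 10% stopping or less with early onset, the excess over chance is small.
- **That a hazard which halves after treatment ends is also a null case.** It is not: being on treatment then truly raises risk. With a 28-day risk of 30%, the Day 112 risk is 1 − 0.7^4 = 0.76 after 112 days of treatment and 1 − 0.7^(1 + 84/56) = 0.59 after 28 days, a real ratio of 1.29. Larger ratios from such a model mix effect and bias.
- **That patients beyond 16 weeks vanish from all duration analyses.** Long-term treatment holds them, and 8.2.2 tabulates them.
- **That mean maintenance dose and concomitant drugs are shown to be distorted in the same way.** They too can change after baseline, but nothing here shows a comparable bias, and dose is a named question in Protocol 7.3.9.

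**Conclusion.** Both parts hold on the text. The missing level is a plain mismatch between SAP 5.4 and 8.2.2, confined to Treatment period. The duration risk ratios cannot be read as evidence about risk: with no true effect they fall on either side of 1, depending on when reactions occur and how often they stop treatment. The direction of the problem follows from Protocol 7.3.6 and SAP 8.2.3. The sizes rest on assumed durations, onset patterns and stopping shares, and for the six-level factor on an assumed reference level. The six-level factor is the more exposed, since the counting window alone can give 2.2-2.5. No formal decision is at risk; the consequence is that a subgroup table may be misread. The change should be made, and it is not critical.

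**What to change.** 1. Add a >16 weeks level to both Treatment period lists in SAP 5.4, matching 8.2.2.
2. Keep counts and proportions by Treatment period and Long-term treatment, for safety and for clinical response. Drop the risk ratios and risk differences (and their plot) for these two factors, and remove both from the 8.2.3.5 screen.
3. In the onset-interval table of SAP 8.2.3.1, which now covers only major items and reactions seen in at least 10% of patients, add a row for any adverse drug reaction and show patient-weeks at risk in each interval. Count time from Day 1 to the earliest of the first reaction in that row, end of treatment plus 28 days, or Day 112. Include days of suspension, as the treatment-period definition in 8.2.2 does.

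The cost is SAP wording and a little programming from dates already recorded. There will be fewer risk ratios, and the interval rates show when reactions occur without comparing long with short treatment. A footnote on the existing ratios would be a smaller change, but it would leave both factors in the screen.

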7.2.1. Inclusion criteria

1. Patients under the age of 15 years at the initiation of treatment with this product
2. Patients with invasive fungal infections

The indications, and dosage and administration of this product are as follows. The latest package insert should be referred to when administering this product.

[INDICATIONS]

Severe mycosis as follows:

- Invasive aspergillosis, Pulmonary aspergilloma, Chronic necrotic pulmonary aspergillosis.
- Candidemia, Esophageal candidiasis*, Candidal peritonitis, Bronchopulmonary candidiasis.
- Cryptococcal meningitis, Pulmonary cryptococcosis.
- Fusariosis.
- Scedosporiosis. * Only for tablets and dry syrup

[DOSAGE AND ADMINISTRATION]

<for Intravenous Use>

Adult	Voriconazole is administered by intravenous drip infusion at the dose of 6 mg/kg twice daily on day 1 and 3 mg/kg or 4 mg/kg twice daily from day 2 onward.
Children (Aged 2 to <12 and ≥12 whose body weight is less than 50 kg)	9 mg/kg as voriconazole twice daily on day 1 and 8 mg/kg twice daily from day 2 should be given intravenously. Dose may be increased if poorly responded by 1 mg/kg at a time, and dose in intolerant patients should be reduced by 1 mg/kg at a time.
Children (Aged ≥12 whose body weight is 50 kg or more)	6 mg/kg as voriconazole twice daily on day 1 and 4 mg/kg twice daily from day 2 should be given intravenously.

<Tablet>

Adult (body weight ≥40 kg)	A recommended oral dose of voriconazole is 300 mg/dose twice daily between meals on day 1, and 150 or 200 mg/dose twice daily between meals on day 2 and thereafter. Dose may be increased depending on condition of patients or if poorly responded; provided that a total daily dosage should not exceed 400 mg/dose twice daily on day 1 and 300 mg/dose twice daily on day 2 and thereafter.
----------------------------	--

Adult (body weight <40 kg)	A recommended oral dose of voriconazole is 150 mg/dose twice daily between meals on day 1, and 100 mg/dose twice daily between meals on day 2 and thereafter. Dose may be increased from day 2 onward depending on condition of patients or if poorly responded; provided that a total daily dosage should not exceed 150 mg/dose twice daily.

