Children (Aged 2 to <12 and ≥12 whose body weight is less than 50 kg)	After the administration of Voriconazole injection, a recommended maintenance oral dose of voriconazole following injection therapy is 9 mg/kg/dose twice daily between meals. Dose may be increased by 1 mg/kg at a time if poorly responded, and dose in intolerant patients should be reduced by 1 mg/kg at a time (unless the dosage was at its maximum 350 mg, in which case, dose should be reduced by 50 mg at a time). A total daily dosage should not exceed 350 mg/dose twice daily.
Children (Aged ≥12 whose body weight is 50 kg or more)	After the administration of Voriconazole injection, a recommended maintenance oral dose of voriconazole following injection therapy is 200 mg/dose twice daily between meals; which may be increased up to 300 mg/dose twice daily if poorly responded.

<Dry Syrup>

Adult (body weight ≥40 kg)	A recommended oral dose of voriconazole is 300 mg/dose twice daily between meals on day 1, and 150 or 200 mg/dose twice daily between meals on day 2 and thereafter. Dose may be increased depending on condition of patients or if poorly responded; provided that a total daily dosage should not exceed 400 mg/dose twice daily on day 1 and 300 mg/dose twice daily on day 2 and thereafter.
Adult (body weight <40 kg)	A recommended oral dose of voriconazole is 150 mg/dose twice daily between meals on day 1, and 100 mg/dose twice daily between meals on day 2 and thereafter. Dose may be increased from day 2 onward depending on condition of patients or if poorly responded; provided that a total daily dosage should not exceed 150 mg/dose twice daily.
Children (Aged 2 to <12 and ≥12 whose body weight is less than 50 kg)	After the administration of Voriconazole injection, a recommended maintenance oral dose of voriconazole following injection therapy is 9 mg/kg/dose twice daily between meals. Dose may be increased by 1 mg/kg at a time if poorly responded, and dose in intolerant patients should be reduced by 1 mg/kg at a time (unless the dosage was at its maximum 350 mg, in which case, dose should be reduced by 50 mg at a time). A total daily dosage should not exceed 350 mg/dose twice daily.

Children (Aged ≥ 12 whose body weight is 50 kg or more)	After the administration of Voriconazole injection, a recommended maintenance oral dose of voriconazole following injection therapy is 200 mg/dose twice daily between meals; which may be increased up to 300 mg/dose twice daily if poorly responded.

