7.3.2. Targeted drug use record

The following will be recorded for the treatment status of this product.

- (1) Dosage form
- (2) Dose
- (3) Body weight used for calculation of adjustment of this product
- (4) Frequency of dose
- (5) Treatment period

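### The mg/kg dose categories have their edges on the printed weight-based doses of 6, 8 and 9 mg/kg, so any rounding down of the mg dose splits children on one nominal dose between two categories

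*SAP*

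**What the plan says.** **Categories.** SAP 5.4 lists two dose factors with identical limits, once for safety and once for clinical response:
- "Dose on the first day (mg/kg) [<6, ≥ 6 to <7, ≥ 7 to <8, ≥ 8 to <9, ≥ 9 to <10", then 10 and above, and unknown;
- "Mean maintenance dose (mg/kg) [<6, ≥ 6 to <7, ≥ 7 to <8, ≥ 8 to <9, ≥ 9 to <10", then 10 and above, and unknown.

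The lower edge belongs to the category. SAP 8.2.2 repeats these limits in the treatment-status tables, where maintenance dose is also given for injection alone and for oral forms alone.

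**Use.** SAP 8.2.3.4 tabulates patients with any adverse drug reaction, and with any serious one, by each 5.4 factor, with risk ratios and risk differences as in 8.1.3. SAP 8.2.3.5 tabulates reactions further for any factor with a risk ratio of at least 2 or at most 0.5. SAP 8.2.4.4 applies the factors to clinical response.

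**Printed pediatric doses (protocol 7.2.1).**
- Intravenous, age 2 to under 12, or 12 and over and under 50 kg: "9 mg/kg as voriconazole twice daily on day 1 and 8 mg/kg twice daily from day 2 should be given intravenously", with changes of 1 mg/kg at a time.
- Intravenous, age 12 and over and at least 50 kg: "6 mg/kg as voriconazole twice daily on day 1 and 4 mg/kg twice daily from day 2 should be given intravenously".
- Oral, first group: "a recommended maintenance oral dose of voriconazole following injection therapy is 9 mg/kg/dose twice daily between meals", capped at 350 mg per dose.
- Oral, second group: "a recommended maintenance oral dose of voriconazole following injection therapy is 200 mg/dose twice daily between meals".

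Protocol 7.3.2 records the body weight used to calculate the dose. The SAP gives no tolerance, no rounding rule for the calculated mg/kg, no choice of weight as denominator and no formula for the mean maintenance dose.

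**The concern.** A category edge should lie where few patients are expected. Here the edges lie where patients on the printed weight-based doses are expected to cluster. A nominal 9 mg/kg belongs in 9 to <10 only if the dose given is not a fraction below 9; otherwise the child moves to 8 to <9. The same holds at 6 and 8 mg/kg, and at stepped values such as 7 and 10 mg/kg. A child on 8 mg/kg whose dose is rounded down shares a category with a child whose dose was truly reduced by one step.

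Factors affecting safety and effectiveness are a stated objective (protocol 6, SAP 2.2), and dose is one of the factors examined. If adjacent categories hold children on the same nominal dose, their risk ratios partly compare rounding noise. A real relation with dose is then blurred, and the screen in SAP 8.2.3.5 works on diluted contrasts. The target is 100 patients over seven levels, and risk ratios are withheld for small groups (SAP 8.1.3), so splitting one regimen also thins the cells.

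**Working it through.** The documents state no figure on this point, so there is none to reproduce.

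**Inputs from the documents.** Edges 6, 7, 8, 9 and 10 mg/kg, lower edge included (SAP 5.4). Printed doses 6, 8 and 9 mg/kg, step 1 mg/kg, oral cap 350 mg (protocol 7.2.1). Tablets of 50 and 200 mg (protocol title table).

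**Assumptions.** Weights evenly spread in 0.1 kg steps over 8 to 50 kg (50 to 70 kg for 6 mg/kg). Dose rounded to 1, 5, 10 or 50 mg, ties upward. mg/kg read as per administration; the SAP does not say, but its overdose footnote (over 350 mg and at least 10 mg/kg for injection) points that way.

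**Formula.** Received mg/kg = round(nominal × weight) / weight, then placed in the SAP categories.

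**Example, nearest 5 mg.**
- 17 kg at 8 mg/kg: 136 → 135 mg; 135/17 = 7.94, in 7 to <8.
- 18 kg at 8 mg/kg: 144 → 145 mg; 145/18 = 8.06, in 8 to <9.
- 18 kg at 9 mg/kg: 162 → 160 mg; 160/18 = 8.89, also in 8 to <9.

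**Why the share is near one half.** For nominal 9 mg/kg, 9 × weight takes every 0.1 mg remainder about equally often. To the nearest 1 mg, remainders 0.1 to 0.4 go down: 4/10 = 40%. To the nearest 5 mg, 0.1 to 2.4: 24/50 = 48%. To the nearest 10 mg, 0.1 to 4.9: 49/100 = 49%.

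**Below the nominal category, current edges (enumerated over all weights, no oral cap).**

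| Rounding | Nominal 6 | Nominal 8 | Nominal 9 |
|---|---|---|---|
| none | 0% | 0% | 0% |
| nearest 1 mg | 40% | 40% | 40% |
| nearest 5 mg | 48% | 48% | 48% |
| nearest 10 mg | 48% | 48% | 49% |
| down to 1 mg | 80% | 80% | 90% |
| down to 5 mg | 96% | 96% | 98% |
| down to 10 mg | 98% | 96% | 99% |

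**In the nominal category, half-unit edges.** Nearest 1, 5 or 10 mg: at least 99%. Down to 10 mg: about 92% for nominal 8 and 9.

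**50 mg steps, nearest.** For nominal 8 and 9 mg/kg, about 58% stay in category with half-unit edges, against about 44% to 45% now. Over 10 to 38.8 kg the half-unit figure is about 50%.

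**Oral cap, no rounding.** 350/9 = 38.9 kg and 350/8 = 43.75 kg. A nominal 9 mg/kg child between these weights falls in 8 to <9, and one above 43.75 and under 50 kg in 7 to <8. With half-unit edges, 350/8.5 = 41.2 kg, and (50 − 41.2)/42 = 21% fall below 8.5.

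**Mixing of 8 and 9 mg/kg.** With equal numbers on each, weights of 10 to 38.8 kg and nearest 1, 5 or 10 mg, 40% to 48% of the 8 to <9 category comes from nominal 9 mg/kg.

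**The case against.** - **The categories sort received dose, and do so correctly.** A child who got 8.9 mg/kg belongs in 8 to <9, and any cut separates near-equal values. This stands: nothing is misfiled. The weakness is that these cuts fall where received doses are expected to cluster.
- **The rounding is assumed.** This stands for the size. The direction is arithmetic: any rounding down from an edge crosses it. Whole tablets come in 50 mg steps, so exact mg/kg dosing cannot be presumed.
- **Half-unit edges are no full cure.** This stands for 50 mg tablet steps and the oral cap. They also cut at 8.5, so a child switched from 8 mg/kg intravenous to 9 mg/kg oral may fall on either side.
- **The study is exploratory.** This stands. SAP 4.1 says it is not confirmatory, and 8.2.2 keeps continuous mg/kg summaries and separate route tables. Those tables do not feed the 5.4 risk ratios.

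A reader might infer more than the documents support:
- *That all printed doses lie on an edge.* The 4 mg/kg intravenous dose and the fixed 200 mg oral dose do not.
- *That the 8 and 9 mg/kg regimens are mixed throughout.* For first-day dose the printed intravenous values are 9 and 6 mg/kg, so the problem there is splitting. Mixing mainly concerns mean maintenance dose, because intravenous (8) and oral (9) are pooled.
- *That ignoring the recorded dosing frequency distorts the categories.* Every printed pediatric regimen is twice daily, so this is speculative.

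**Conclusion.** The point holds as a weakness in an exploratory analysis. The edges coincide with the printed weight-based doses of 6, 8 and 9 mg/kg and with the 1 mg/kg steps, so rounding down splits children on one nominal dose. Under the stated weight assumption, about 40% to 49% fall one category low with rounding to the nearest 1, 5 or 10 mg, and 80% to 99% fall below with rounding down. With exact dosing the figure is zero. The percentages depend on assumptions that the documents neither confirm nor exclude; the coincidence of edges and doses does not.

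The effect is limited to the dose subgroups for any reaction, serious reactions and clinical response, and to the risk-ratio screen. It would be too strong to conclude that the plan cannot distinguish the regimens at all, since the continuous and route-specific tables in SAP 8.2.2 remain. The point concerns analysis categories only and does not judge any dose.

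**What to change.** In SAP 5.4 (safety and clinical response) and 8.2.2, replace the mg/kg limits with half-unit edges: <5.5, 5.5 to <6.5, 6.5 to <7.5, 7.5 to <8.5, 8.5 to <9.5, 9.5 to <10.5, ≥10.5, unknown. State that mg/kg is per administration and uses the dosing weight recorded under protocol 7.3.2(3).

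Leave the overdose definition in the SAP 5.4 footnote unchanged and derive it separately, since its 10 mg/kg limit now falls inside a category. Read the maintenance-dose subgroups alongside the injection-alone and oral-alone tables in 8.2.2, because new edges do not undo the pooling of routes.

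**Cost.** SAP wording and reprogrammed limits; no new data. Comparability is lost with any table already made on the old limits, though both versions can be shown. Children switched from intravenous to oral treatment may fall on either side of 8.5, and the tablet-step and oral-cap effects remain and should be noted with the results.
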